2.2 ABI-4334

2.2.1 Description

ABI-4334 is an orally administered, potent and selective, next-generation, small molecule inhibitor of HBV core protein. ABI-4334 interferes with essential functions of the HBV core protein, and therefore inhibits HBV replication by different mechanisms than NrtIs or IFN α . ABI-4334 binds to the HBV core protein, and induces altered, non-functional core protein assembly in preclinical models. Thus, inhibition of HBV core protein functions by ABI-4334, when used in combination with currently approved HBV antivirals, offers the potential to improve therapy for cHBV and provide patients with enhanced rates of durable off-treatment virologic responses following a finite treatment period.

Refer to the Investigator's Brochure (IB) for detailed information on ABI-4334.

2.2.2 Nonclinical Studies

2.2.2.1 In-vitro Activity

In primary human hepatocytes, ABI-4334 exhibited potent antiviral activity against HBV replication (0.5 nM). Furthermore, ABI-4334 potently inhibited the formation of HBV cccDNA (2.4 nM), which is distinct from the mechanisms of action of NrtIs. ABI-4334 is pan-genotypic, with activity across HBV genotypes A-J. No cytotoxicity was observed with ABI-4334 across

multiple cell types and cell lines and the activity is specific to HBV. ABI-4334 remains fully active against a panel of NrtI-resistant viruses. A panel of 16 core inhibitor binding pocket variants were evaluated for sensitivity to ABI-4334; 1 of 16 variants exhibited > 10-fold reduced susceptibility to ABI-4334. Combination studies with ABI-4334 and NrtI (ie, tenofovir [TFV] or entecavir [ETV]) demonstrated additive effects.

Refer to the IB for results from other nonclinical studies, including pharmacology, pharmacokinetics, and toxicology.

2.2.3 Clinical Studies

No clinical studies have been conducted with ABI-4334.

2.3 Study Rationale

Chronic hepatitis B virus infection is a major cause of liver-related morbidity and mortality affecting approximately 296 million people worldwide. While therapy with NrtI is able to achieve adequate viral suppression in most HBeAg negative patients and three quarters of HBeAg positive patients after 1 year, SVR and loss of HBsAg are rare (< 5%). Novel agents, administered alone or in combination with other therapies, are likely required to provide durable off-treatment virologic responses.

ABI-4334 is one such agent, which following oral administration, provides potent and selective inhibition of the HBV core protein. Through interference with the essential functions of the HBV core protein, ABI-4334 inhibits HBV replication by orthogonal mechanisms distinct from NrtIs or IFN α . Thus, when used in combination with currently approved or other investigational HBV antivirals or immune modulators, ABI-4334 offers the potential to improve therapy for cHBV and provide patients with enhanced rates of durable off-treatment virologic responses following a finite treatment period.

Study of ABI-4334-101 is a first-in-human (FIH) study assessing the safety, tolerability, and pharmacokinetics (PK) of single- (Part A; SAD) and multiple-ascending doses (Part B; MAD) of ABI-4334 in healthy subjects.

2.3.1 Rationale for Dose Selection

The starting dose for the proposed Phase 1 FIH clinical study has been determined based on the United States (US) Food and Drug Administration (FDA) guideline on estimating the maximum safe starting dose in initial clinical trials for therapeutics in adult healthy volunteers ([FDA 2005](#)) and the European Medicines Agency's (EMA) guideline on strategies to identify and mitigate risks for first-in-human clinical trials with investigational medicinal products ([EMA 2018](#)).

The conclusions from the 28-day repeat-dose Good Laboratory Practices (GLP) toxicology studies were that the no observed adverse effect level (NOAEL) in rats was 300 mg/kg/day, and the no observed effect level (NOEL) in dogs was 30 mg/kg/day (the highest doses tested). Defining the "most appropriate species" as the one that produces the lowest HED, the dog NOEL of

30 mg/kg/day and corresponding HED of 16.7 mg/kg, or approximately 1000 mg for a 60 kg human subject, have been used to calculate the starting dose for the proposed FIH clinical study. Using the standard safety factor of 10 discussed in the FDA guideline (FDA 2005) results in a maximum recommended starting dose of 100 mg. To provide an additional margin of safety, a starting dose of 30 mg is proposed for the initial cohort of healthy subjects in Part A of this study. Thus, the actual safety factor for the proposed starting dose in this study is approximately 33. The ratio of the HED to the proposed starting dose is shown in Table 1.

Table 1. Assumed NO(A)EL Doses in Nonclinical Species and Proposed Clinical Dose

Species	NO(A)EL (mg/kg/day)	ABI-4334 PK Parameter		HED ^b (mg/kg)	HED ^c (mg)	MRSD ^d (mg)	Proposed Starting Dose	Safety Factor for Proposed Starting Human Dose ^f
		C _{max} ^a (ng/mL)	AUC ₀₋₂₄ ^a (ng*hour/mL)					
Rat	300	36,100	424,000	48.4	2900	290	NA	NA
Dog	30	15,900	183,500	16.7	1000	100	30 ^e	33

Abbreviations: HED = human equivalent dose; MRSD = maximum recommended starting dose; NA = not applicable; NO(A)EL = no observed (adverse) effect level; PK = pharmacokinetics

^a Day 28 parameters, averaged for males and females

^b Determined according to the FDA guidance, Estimating the Safe Starting Dose in Clinical Trials for Therapeutics in Adult Healthy Subjects; conversion factor of 1.8 for dog and 6.2 for the rat.

^c Assumes 60 kg human.

^d Using the standard safety factor of 10.

^e The dog was considered the most appropriate species for calculating the starting dose in this FIH study.

^f Ratio of the HED to the proposed starting dose for this FIH study.

The maximum dose in the study will not exceed the exposures in dogs at the NOEL dose of 30 mg/kg/day (maximum observed plasma concentration [C_{max}] of 15900 ng/mL or area under the concentration-time curve [AUC] of 183,500 ng*hour/mL). Although the maximum doses correspond to approximately 1800 mg/day based on C_{max} and 2400 mg/day based on AUC using current human predictions, doses higher than 1000 mg/day will not be administered in this study. Therefore, the maximum dose of ABI-4334 to be evaluated in this study will not exceed the exposures observed in dogs at the NOEL dose of 30 mg/kg/day, or 1000 mg/day, whichever is lower.

2.4 Risk-Benefit Profile

ABI-4334 is being developed for the treatment of cHBV. Since this is a FIH study of ABI-4334, the therapeutic potential of ABI-4334 is yet to be determined. Nonclinical data generated with ABI-4334 as well as clinical data from other core inhibitors in development suggest that, as compared to monotherapy with NrtIs, there may be several potential benefits of ABI-4334 either alone or in combination with NrtIs for the treatment of cHBV. These include:

- Greater on-treatment antiviral activity in combination (more rapid suppression of HBV replication) compared to current NrtI alone
- Greater inhibition of HBV cccDNA establishment and thus greater loss of HBV cccDNA over time as compared to current NrtI alone
- Potential for finite therapy as compared to NrtIs which are often lifelong therapies

In the 28-day GLP-compliant oral repeat-dose toxicity studies, ABI-4334 was well-tolerated at doses up to 300 mg/kg/day in rats, and in dogs up to 30 mg/kg/day, the highest doses tested. In rats, there were no drug-related clinical signs or changes in body weights, food consumption, nor changes in clinical pathology data. Non-adverse ABI-4334-related findings were limited to the adrenal gland. In dogs, there were no ABI-4334-related findings at any dose tested. There were no drug-related clinical signs or changes in body weights, food consumption, nor changes in clinical, gross, or histopathology data. Therefore, following daily oral doses for 28 days, the NO(A)ELs for the rat and the dog are 300 mg/kg/day ($AUC \leq 455,000 \text{ ng*hour/mL}$) and 30 mg/kg/day ($AUC \leq 185,000 \text{ ng*hour/mL}$), respectively (the highest doses tested).

During the conduct of this study to help ensure subject safety, a data review committee (DRC) and the enrolling study Investigator will perform ongoing safety data reviews of the frequent clinical and laboratory assessments, as defined in the DRC charter.

No therapeutic benefit is anticipated for the healthy subjects participating in this study. Any potential benefit is anticipated to be limited to the no-cost clinical and laboratory evaluations associated with the study, and the possibility that ABI-4334 could potentially benefit patients with cHBV in the future if additional studies establish ABI-4334 as a therapeutic advance for patients with cHBV.

Overall, the risk-benefit profile of ABI-4334 is favorable.

3 STUDY OBJECTIVES AND ENDPOINTS

3.1 Study Objectives

3.1.1 Primary Objective

The primary objective of this study is:

- To assess the safety and tolerability of orally administered ABI-4334 in healthy subjects following single (Part A, SAD) and 8-day multiple (Part B, MAD) oral doses

3.1.2 Secondary Objectives

The secondary objectives of this study are:

- To characterize the PK of ABI-4334 in plasma following single doses and 8-day multiple doses in healthy subjects
- To evaluate the effect of food on the PK of ABI-4334 following a single dose in healthy subjects (Part A food-effect cohort(s) only)

3.1.3 Exploratory Objective

The exploratory objective of this study is:

- To evaluate the PK of ABI-4334 in urine following 8-day multiple doses in healthy subjects (Part B, MAD)

3.2 Study Endpoints

3.2.1 Primary Endpoint

The primary endpoint is:

- Proportion of subjects with adverse events (AEs), premature treatment and study discontinuation due to AEs, and abnormal laboratory results (for each part)

3.2.2 Secondary Endpoints

The secondary endpoints are:

- Noncompartmental plasma PK parameters such as AUC_{last} , AUC_{0-inf} , AUC_{tau} , C_{max} , T_{max} , C_{trough} , k_{el} , $t_{1/2}$, CL/F , V_z/F , dose normalized AUCs and C_{max} , accumulation ratios and linearity factor (as applicable for each part)
- Comparison of AUC and C_{max} between fasted and fed treatments (Part A, SAD, food effect cohorts only)

3.2.3 Exploratory Endpoint

The exploratory endpoint is:

- Noncompartmental urine PK parameters such as A_e , A_{e0-24} , CL_r , %Fe (Part B, MAD)

4 STUDY DESIGN

4.1 Overview

This is a Phase 1, FIH, randomized, blinded, placebo (PBO)-controlled, single- and multiple-dose, dose escalation study of ABI-4334 in healthy subjects. Part A is designed to assess the safety, tolerability, and PK profile of ABI-4334 following SAD in healthy subjects, as well as the effect of food on ABI-4334. Part B is designed to assess the safety, tolerability, and PK profile of ABI-4334 following MAD in healthy subjects. [Figure 1](#) provides an overview of the 2-Part study design.

Figure 1. Overview of Study Design – Parts A & B (SAD and MAD)

- Cohort A1: 30 mg ABI-4334 or PBO, orally fasted
 - Cohort A2: TBD mg fasted
 - Cohort A3: TBD mg fasted
 - Cohort A4: TBD mg fasted
 - Cohort A5: TBD mg fasted
 - Cohort A6: Food effect cohort, TBD mg, fed
 - Cohort A7: Food effect cohort, TBD mg (2-period crossover: fasted & fed)
- Cohort B1: TBD mg
 - Cohort B2: TBD mg

Abbreviations: BID=twice daily; MAD=multiple ascending dose; PBO=placebo; PO=orally by mouth; QD=once daily; SAD=single ascending dose; TBD=to be determined

*Applies to all SAD cohorts, except Cohort A7, which will only have 6 active subjects (ie, randomized to ABI-4334), no PBO subjects.

**Part B dosing may commence prior to Part A being completed.

[figure not shown]
4.1.1 Part A (SAD in Healthy Subjects)

Part A of the study will enroll up to 5 fasted cohorts, ie, Cohorts A1-A5, and up to 2 fed cohorts to evaluate food effect, ie, Cohort A6 (with subjects from a previous fasted cohort), and an additional cohort, ie, Cohort A7, if needed (with new subjects).

The first cohort of Part A, ie, Cohort A1, will evaluate a single dose of 30 mg ABI-4334 ([Figure 2](#)). Dose levels for subsequent cohorts will be determined based on interim cohort review performed by an unblinded DRC (see [Section 10.6](#) for details on DRC procedures) between SAD cohorts for purposes of dose escalation. Study data will include safety data from Day 1 through Day 4 for the present cohort and all available safety data for preceding cohorts. In addition, PK

data through 24 hours after dosing for the present cohort and available PK data for preceding cohorts will be reviewed. In no case would a dose escalation be greater than 3.3-fold compared with the previous dose. The maximum dose of ABI-4334 to be evaluated in Part A (SAD) will not exceed the exposures observed in dogs at the NOEL dose of 30 mg/kg/day, or 1000 mg/day, whichever is lower.

Figure 2. Study Design Schematic – Part A (SAD in Healthy Subjects)

Abbreviations: DRC=Data Review Committee; PBO=placebo; SAD=single ascending dose

Each of the Cohorts A1-A5 will enroll 8 healthy subjects who will be randomized in a 6:2 ratio to receive a single oral dose of the study drug, ie, ABI-4334 (6 subjects) or PBO (2 subjects) in a fasted state, followed by a 7-day follow-up period. Subjects will remain confined to the study clinic from Days -1 to 4, with outpatient follow-up visits, as specified in [Appendix 1](#). Dosing of a subsequent SAD cohort can begin at least 8 days after dosing of the sentinel subjects from the previous cohort (see below).

Because this is a FIH study, a sentinel dosing approach will be utilized for each Cohort A1-A5, where initially only 2 subjects per cohort will be dosed (one receiving ABI-4334 and one receiving PBO). These sentinel subjects will be observed for a minimum of 3 days postdose to ensure acceptable tolerability of the study drug, as determined by the DRC, before dosing of the remaining subjects within the cohort can proceed.

The DRC will select a single dose level from Cohorts A1-A5 for evaluation of food effect. The selection of this dose level can be made prior to completion of all fasted SAD cohorts and will be based on a preliminary evaluation by the DRC of the available safety, tolerability, and PK data from selected Cohorts A1-A5. Subjects who complete participation in this selected cohort will be asked to return to the study site to be enrolled into the food-effect cohort (ie, Cohort A6), following a minimum of 7-day washout period since their last study drug dose. While Baseline evaluations will be conducted prior to dosing in Cohort A6, repeat assessment of all study eligibility criteria will not be performed. Returning subjects will retain their original subject number and randomized treatment assignment. After the Day 7 visit in the original cohort (from Cohort A1-A5), the study

drug will be administered 30 minutes after the complete consumption of a high fat meal (approximately 50% calories from fat).

If there is an insufficient number of subjects from previous fasted SAD cohorts (ie, A1-A5), who are willing to participate in Cohort A6, then a separate Cohort A7 may be enrolled, comprising 6 new subjects meeting the study eligibility criteria, who will all receive ABI-4334. Cohort A7 will involve a two-period crossover assessment of food effect (ie, Period 1: dosing under fasted or high fat-fed conditions; Period 2: dosing under condition opposite of Period 1), with a minimum 7-day washout period between dosing in Period 1 and Period 2, and a 7-day postdose follow-up in Period 2.

Details on PK sampling for Part A (SAD) are provided in [Section 8.4](#) and [Appendix 1](#).

4.1.2 Part B (MAD in Healthy Subjects)

[figure not shown]
Part B dosing may commence prior to Part A being completed. The dose level and dosing schedule for the first cohort of Part B, ie, Cohort B1, will be determined based on emergent safety, tolerability, and PK data from completed Part A cohorts, with the daily dose at least 2-fold lower than a Part A dose level deemed safe and tolerable.

Both cohorts planned for Part B, ie, Cohort B1 and Cohort B2, will enroll 8 healthy subjects who will be randomized in a 6:2 ratio to receive oral daily doses of the study drug, ie, ABI-4334 (6 subjects) or PBO (2 subjects), for 8 consecutive days, followed by a 7-day follow-up period ([Figure 3](#)). Dosing may occur under fasted or fed conditions, depending on the results from the food-effect cohorts in Part A. Subjects will remain confined to the study site from Days -1 to Day 11 (ie, 3 days post last day of dosing), with outpatient follow-up visits, as specified in [Appendix 2](#).

The dose level and dosing schedule for Cohort B2 will be based on an evaluation by the DRC of safety data from Day 1 through Day 8 for Cohort B1 and all available safety data for preceding cohorts. In addition, PK data through 24 hours after dosing on Day 8 for Cohort B1 and available PK data for preceding cohorts will be reviewed. In no case would the dose escalation be greater than 3.3-fold compared with the previous dose. Dosing of Cohort B2 can begin at least 11 days after the first day dosing of subjects in Cohort B1. The maximum dose of ABI-4334 to be evaluated in Part B (MAD) will not exceed the exposures observed in dogs at the NOEL dose of 30 mg/kg/day, or 1000 mg/day, whichever is lower.

Details on PK sampling for Part B (MAD) are provided in [Section 8.4](#) and [Appendix 2](#).

Figure 3. Study Design Schematic – Part B (MAD in Healthy Subjects)

Abbreviations: DRC=Data Review Committee; PBO=placebo

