1 SYNOPSIS

Protocol Title	A Phase 1, Blinded, Placebo-controlled Study of the Safety, Tolerability, Pharmacokinetics of Single- and Multiple-Ascending Doses of ABI-4334 in Healthy Subjects
Protocol Number	ABI-4334-101
Test Product, Dose, and Mode of Administration	
ABI-4334 will be provided as 10 mg and 50 mg tablets for oral, by mouth (PO) administration.
 
Part A (Single-ascending dose [SAD] in Healthy Subjects)
 
 • Cohort A1: 30 mg ABI-4334 or matching placebo (PBO), PO, single dose, fasted • Cohort A2: to be determined (TBD) mg ABI-4334 or PBO, PO, single dose, fasted • Cohort A3: TBD mg ABI-4334 or PBO, PO, single dose, fasted • Cohort A4: TBD mg ABI-4334 or PBO, PO, single dose, fasted • Cohort A5: TBD mg ABI-4334 or PBO, PO, single dose, fasted • Cohort A6: Food effect cohort with subjects from a previous fasted cohort, TBD mg ABI-4334 or PBO, PO, single dose, fed • Cohort A7: Additional food effect cohort (if needed), TBD mg ABI-4334, PO, single dose, 2-period crossover (fasted & fed) 
Part B (Multiple-ascending dose [MAD] in Healthy Subjects: 8-Day Dosing Duration)
 
 • Cohort B1: TBD mg ABI-4334 or PBO, PO, multiple doses • Cohort B2: TBD mg ABI-4334 or PBO, PO, multiple doses 
The dose level for Part A (SAD) Cohort A1 is defined. The dose levels for subsequent cohorts and once daily (QD) or twice daily (BID) dosing schedule for Part B (MAD) will be selected based on evaluation of safety, tolerability, and available pharmacokinetics (PK) from the previous cohorts. In no case would each individual dose escalation be greater than 3.3-fold compared with the previous dose. Some prespecified cohorts may not be enrolled.

Reference Therapy, Dose, and Mode of Administration	Matching placebo tablets for oral administration will be supplied for each ABI-4334 dosage strength. The dosing schedule will follow that of ABI-4334 for the respective cohort.
Target Population	Healthy male or female subjects
Phase	1
Number of Subjects Planned	Part A (SAD): Up to 46 (approximately 8 subjects/Cohorts A1-A6; 6 subjects/Cohort A7 [Note: Cohort A6 will enroll returning subjects from a previous SAD cohort])

	Part B (MAD): Up to 16 (approximately 8 subjects/cohort)
Study Sites and Location	A single site in New Zealand
Treatment Duration	Part A (SAD): 1 day Part B (MAD): 8 days

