6.1.1.4 Dosage and Administration

Study drug doses will be administered with 240 mL of water in the clinic under supervision. Subjects will remain in an upright or sitting position for at least 30 minutes after ingestion unless a semi-recumbent or recumbent position is required for ECGs or vital signs. Water, other than for drug administration, will be restricted for 1 hour before and 1 hour after each oral dose. After study drug administration, site personnel will perform a hand and mouth check to verify that the administered dose was swallowed.

If the PK results for Part A Cohorts A1-A5 indicate that BID dosing should be assessed, then subjects in one or both of the Part B Cohorts ie, B1-B2, may receive their study drug as two divided doses, separated by approximately 12 hours on the dosing days.

Fasting requirements for dosing are described below.

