10.6 Data Review Committee

10.6.1 Overview of Data Review Committee

The DRC will review data as described in [Section 10.6.2](#). Other designated unblinded team members may participate in the DRC review meetings, as required.

For each interim cohort review, study data will include safety data from Day 1 through Day 4 (Part A, SAD cohorts) or Day 1 through Day 8 (Part B, MAD cohorts) for the present cohort and all available safety data for preceding cohorts. In addition, PK data through 24 hours after dosing (SAD cohorts) or from the first 24 hours after dosing on Day 8 (MAD cohorts) for the present cohort and available PK data for preceding cohorts will be reviewed.

The DRC will make recommendations for dose level and dosing schedule, as per below:

- Continue with the next cohort at a higher or lower dose, OR
- Repeat a dose, OR
- Modify the next cohort(s), including addition of assessments or procedures, OR
- Discontinue a cohort, OR
- Discontinue the study

A decision to reduce the dose in the next cohort may be made for either safety findings (if there is a concern for a dose related toxicity), or to fully evaluate the PK.

A decision to increase the dose in the next cohort may be made if the dose under evaluation is found to be sufficiently safe and well tolerated, and a higher dose is required to fully evaluate the PK.

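### Only Cohort B1 is tied to a dose cleared in Part A; the written limits let B2 reach 1.65 times the single dose behind B1, with no sentinel step written for Part B

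*Combined protocol and SAP*

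**What the plan says.** Protocol 4.1.2 (repeated in the synopsis and in SAP 1.2.2) sets the B1 dose from Part A data, "with the daily dose at least 2-fold lower than a Part A dose level deemed safe and tolerable". For B2, the DRC reviews B1 safety through Day 8, B1 PK to 24 hours after the Day 8 dose, and available data from earlier cohorts. Two numerical limits apply to B2:

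- **Relative cap:** "In no case would the dose escalation be greater than 3.3-fold compared with the previous dose".
- **Absolute ceiling:** dog exposure at the no-effect dose, or 1000 mg/day, whichever is lower.

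The synopsis also has a general cap for all cohorts: "In no case would each individual dose escalation be greater than 3.3-fold compared with the previous dose". Neither sentence says whether dose means total daily dose or dose per administration. Protocol 6.1.1.4 allows a BID schedule, under which Part B subjects "may receive their study drug as two divided doses, separated by approximately 12 hours on the dosing days".

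On timing, 4.1.2 states that "Part B dosing may commence prior to Part A being completed". On sentinels, 4.1.1 states that "a sentinel dosing approach will be utilized for each Cohort A1-A5". The Part B text and Appendix 2 describe no sentinel step. Under 10.6.1, a decision to increase the dose "may be made if the dose under evaluation is found to be sufficiently safe and well tolerated, and a higher dose is required" to characterise the PK fully.

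**The concern.** The B1 rule shows that the sponsor wanted repeat dosing to begin below a single dose already cleared in humans. One permitted escalation step can more than use up that margin, because 3.3 is larger than 2. Nothing in the text then requires the B2 dose to have been given in Part A. The DRC criterion for an increase concerns the dose just studied and the need for PK, not single-dose cover for the next dose.

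This matters because of how Part A handles a new dose. Each goes first to one active and one placebo subject, who are watched for at least 3 days before the rest of the cohort is dosed. Under the written Part B rules, a daily dose higher than any yet given to humans could go to six active subjects without that step, and be repeated for 8 days.

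**Working it through.** **Inputs**

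- B1 daily dose is at most 0.5 x A, where A is the Part A dose behind B1 (4.1.2).
- B2 is at most 3.3 x B1 (4.1.2), read as total daily dose. The divided-dose wording in 6.1.1.4 favours this reading.
- The ceiling is 1000 mg/day or dog no-effect exposure (4.1.2).
- Tablets are 10 mg and 50 mg (synopsis).

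**The plan's own figures (2.3.1)**

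- Human equivalent dose: 30/1.8 = 16.7 mg/kg; x 60 kg = 1000 mg.
- Maximum recommended starting dose: 1000/10 = 100 mg.
- Safety factor at 30 mg: 1000/30 = 33.

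All reproduce. The plan gives no ratio of B2 to a Part A dose.

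**Bound on B2**

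B2 <= 3.3 x 0.5 x A = 1.65 x A, cut off at 1000 mg/day. The cut-off begins at A = 1000/1.65 = 606 mg.

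| Part A dose A (mg) | Largest B1 (mg/day) | Largest B2 (mg/day) | B2/A |
|---|---|---|---|
| 100 | 50 | 165 | 1.65 |
| 300 | 150 | 495 | 1.65 |
| 600 | 300 | 990 | 1.65 |
| 700 | 350 | 1000 | 1.43 |
| 800 | 400 | 1000 | 1.25 |
| 1000 | 500 | 1000 | 1.00 |

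Rounding down to whole 10 mg tablets lowers some ratios. A = 90 gives B1 40, B2 130, ratio 1.44. A = 290 gives 140, 460 and 1.59. A = 600 stays at 1.65.

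**Which ceiling binds**

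Protocol 2.3.1 predicts that dog no-effect exposure corresponds to about 1800 mg/day on Cmax and "2400 mg/day based on AUC using current human predictions, doses higher than 1000 mg/day will not be administered in this study". On those predictions, 1000 mg/day is the operative limit, and it does not bind for A up to 606 mg.

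**Per-administration reading (less supported)**

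A change from QD in B1 to BID in B2 would double the daily multiple to 6.6. That is reachable only for B1 up to 1000/6.6 = 151 mg/day. From 1000/3.3 = 303 mg/day upward, the ceiling allows nothing beyond 3.3-fold. The conclusion does not rely on this reading.

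**Effect of the proposed limit**

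With B2 also held to the highest cleared Part A single dose, B2 divided by that dose is at most 1.0. If that dose is A and B1 = A/2, the largest step from B1 to B2 falls from 3.3-fold to 2.0-fold.

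**Can Part A reach 1000 mg within five fasted cohorts?**

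Yes: 30, 90, 290, 950, 1000 mg. The steps are 90/30 = 3.00, 290/90 = 3.22, 950/290 = 3.28 and 1000/950 = 1.05, all within 3.3.

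**The case against.** The strongest reply is that this is a permissive upper bound, not a planned step. B2 exceeds human experience only if B1 sits near half of A, B2 takes nearly the full step, Part A has not yet reached that level, and the DRC agrees. Part A can advance during B1: a SAD cohort may follow 8 days after the previous sentinels, while B2 waits at least 11 days from B1's first dosing day. All of this is correct, but nothing requires Part A to advance.

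B2 is also not unguarded. The DRC has eight days of B1 data from six active subjects plus everything earlier, the stopping rules in 7.2 apply, and subjects are confined to Day 11. Part A itself allows 3.3-fold jumps above the highest tested dose. These points lower the risk. However, B1 data show tolerability and accumulation at the B1 dose, not at a dose up to 3.3 times larger, and the Part A jumps are single doses that pass through sentinels. The protocol sets hard bounds alongside DRC judgement elsewhere; this one is missing.

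Three technical points stand as qualifications:

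- The 1800 and 2400 mg/day figures are predictions made before any human dosing, so the exposure ceiling could bind earlier.
- The 1.65 is a ratio of doses, not of exposure. Under BID, 495 mg/day is 247.5 mg per administration, below the 300 mg single dose, and peak exposure would depend on accumulation.
- The Figure 3 image and the DRC charter are not in the documents, so the absence of a Part B sentinel step or a further limit rests on the available text.

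**Conclusion.** The concern holds. On the total-daily-dose reading, the written rules allow B2 up to 1.65 times the Part A dose behind B1 when that dose is about 606 mg or less, declining to 1.0 at 1000 mg. This becomes a dose above all human experience only if Part A has not reached the B2 level when B2 starts, which the protocol permits. The size is a dose ratio; the documents give no accumulation or food-effect figure from which to turn it into an exposure ratio. Because the stated rule itself allows the step, this is more than a missing detail and should be changed. The DRC review and stopping rules keep it from being more serious than that.

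**What to change.** Replace the cap sentence in protocol 4.1.2, in the Part B text of the synopsis and in SAP 1.2.2 with:

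*The total daily dose in Cohort B2 will be no greater than 3.3-fold the total daily dose in Cohort B1, and no greater than the highest single dose given in Part A and deemed safe and tolerable by the DRC.*

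This also settles the unit of the Part B cap. The general cap in the synopsis can remain, since the new sentence is compatible with it. The exposure ceiling should stay as well, because a limit in mg does not account for accumulation.

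The cost is one sentence in three places. No dose range is lost if Part A reaches 1000 mg. If Part A stops lower or lags, B2 is held to the cleared single dose. With only two multiple-dose cohorts, that narrowing is a real cost, but it arises only where single-dose cover is lacking.
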